11.6. ECG

Single 12-lead ECGs will be performed at clinic visits as specified in [Table 2](#) Schedule of Assessments.

Summary tables by visit and change from baseline to visit for each ECG parameter (Heart Rate, PR interval, QRS interval, QT interval, RR interval, and QTc interval) will be provided.

The overall results of the ECGs recorded as “normal”, “abnormal, not clinically significant (NCS)” or “abnormal, clinically significant (CS)” will be summarized by treatment group at each visit.

12-lead ECG data will be listed by subject and visit.

The ECG analysis will include a careful review of QTcF values. As part of this review, a summary of the number (percent) of subjects with QTcF values (at pre-treatment and then at any time post-first dose) in the following ranges will be provided: ≤ 450 msec, >450 to ≤ 480 msec, >480 to ≤ 500 msec, and >500 msec. This will be performed by visit as well as at ANY time during the double-blind treatment period (where the highest QTcF value will be used for that assessment).

11.7. Physical Examination

The full physical examination will be conducting at the Screening and Week 13 (or Early Termination) Visits as specified in the Schedule of Assessments. An abbreviated physical examination will be conducted at on Day 1 (Baseline) and Week 14 Follow-Up.

Significant findings prior to the start of dosing will be recorded on the Medical History page of the electronic case report form (eCRF). Only changes from baseline physical examination findings that meet the definition of a treatment-emergent AE will be recorded as an AE.

Physical examination data will be listed only.

11.8. Columbia Suicide Severity Rating Scale (C-SSRS)

The Columbia Suicide Severity Rating Scale (C-SSRS) is a prospective assessment instrument that directly classifies suicidal ideation and behaviour into 11 preferred categories [[Posner 2011](#)]. The C-SSRS involves a series of probing questions to inquire about possible suicidal thinking and behavior.

This document is confidential.

The C-SSRS will be conducted at Screening, Baseline, Week 1 and Week 4, as specified in the [Table 2](#) Schedule of Assessments.

The C-SSRS data will be listed for all subjects. Listings will include behavior type and/or category for Suicidal Ideation and Suicidal Behavior of the C-SSRS.

The following outcomes are C-SSRS categories and have binary responses (yes/no). The categories have been re-ordered from the actual scale to facilitate the definitions of the composite and comparative endpoints, and to enable clarity in the presentation of the results.

- Category 1 – Wish to be Dead
- Category 2 – Non-specific Active Suicidal Thoughts
- Category 3 – Active Suicidal Ideation with Any Methods (Not Plan) without Intent to Act
- Category 4 – Active Suicidal Ideation with Some Intent to Act, without Specific Plan
- Category 5 – Active Suicidal Ideation with Specific Plan and Intent
- Category 6 – Preparatory Acts or Behavior
- Category 7 – Aborted Attempt
- Category 8 – Interrupted Attempt
- Category 9 – Actual Attempt (non-fatal)
- Category 10 – Completed Suicide
- Self-injurious behavior without suicidal intent is also a C-SSRS outcome (although not suicide-related) and has a binary response (yes/no).

Endpoints based on the above categories are defined below.

- Suicidal **ideation**: A “yes” answer at any time during treatment to any one of the five suicidal ideation questions (Categories 1-5) on the C-SSRS.
- Suicidal **behavior**: A “yes” answer at any time during treatment to any one of the five suicidal behavior questions (Categories 6-10) on the C-SSRS.
- Suicidal **ideation or behavior**: A “yes” answer at any time during treatment to any one of the ten suicidal ideation and behavior questions (Categories 1-10) on the C-SSRS.
- Self-injurious behavior without suicidal intent.

A shift table to present changes from pre-treatment to any time post-first-dose will be assessed, with the number (and percent) of subjects showing a worsening from baseline on any of the four endpoints.

The C-SSRS was collected at screening (and the assessment was based on subject recall from the past year), while on-treatment collection was based on outcomes ‘since the prior visit’. Thus, the analysis will be done in two ways:

1. Shifts from screening, where C-SSRS is relative to subject recall of the past year (using Screening value C-SSRS, and shifts to each post-screening time point).

This document is confidential.

2. Shifts from baseline, where C-SSRS is collected relative to subject recall since the PREVIOUS visit, using Baseline value C-SSRS and shifts to each post-baseline time point).

Table 4 presents the general manner in which these data will be tabulated.

Table 4 Sample Table Demonstrating How C-SSRS Outcomes will be Presented

Treatment	Baseline Category	Treatment Category		
		No suicidal ideation or behavior n (%)	Suicidal ideation n (%)	Suicidal behavior n (%)
Drug Name (N=xxx)	No suicidal ideation or behavior	x (%)	x (%)	x (%)
	Suicidal Ideation	x (%)	x (%)	x (%)
	Suicidal Behavior	x (%)	x (%)	x (%)
Comparator Name (N=xxx)	No suicidal ideation or behavior	x (%)	x (%)	x (%)
	Suicidal Ideation	x (%)	x (%)	x (%)
	Suicidal Behavior	x (%)	x (%)	x (%)

Notes: N = number of patients with a baseline and post-baseline C-SSRS assessment, n = number of patients in category. % = 100*n/N.

Baseline refers to [specify definition]

Suicidal Ideation includes any one of the five suicidal ideation events (Categories 1-5). Suicidal behavior includes any one of the five suicidal behavior events (Categories 6-10).

Each patient is counted in one cell only. Patients with both Suicidal Ideation and Suicidal Behavior are included in the Suicidal Behavior category.

A listing of all C-SSRS data will be provided, while a listing of subjects who demonstrated a worsening on any one of the four endpoints will also be provided. These listings will include the Study Day (relative to first dose of double-blind treatment) the C-SSRS was collected.

This document is confidential.

12. Changes from Analysis Planned in Protocol

There were no meaningful changes from the protocol described analysis.

This document is confidential.

13. Reference List

1. Faraone, S.V. Interpreting estimates of treatment effects: implications for managed care. *P T* 33, 700-711 (2008).

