6.2 Subject Inclusion Criteria

1. Males or females between the ages of 55 and 85 years with a clinical diagnosis of early stage AD, defined according to the following criteria assessed prior to randomization:
 - Clinical Dementia Rating (CDR) score of 0.5 or 1, with Memory Box score of 0.5 or greater
 - MMSE score of 20 or greater
 - RBANS DMI score \leq 85

Note: PET imaging for amyloid is not required for diagnosis, which will be made on clinical grounds

2. Currently receiving a stable dose regimen of donepezil or another cholinesterase inhibitor for treatment of AD. Subjects must be receiving a stable dose of a cholinesterase inhibitor for at least 56 days prior to their baseline visit. Doses of these drugs may not be changed during the trial.

Note: Memantine is not permitted during the trial and must be discontinued at least 3 weeks prior to Baseline

3. Modified Hachinski Ischemia score \leq 4.
4. Body mass index (BMI) \leq 38 kg/m², inclusive, and body weight of >48 kg (105 pounds) at screening.
5. Female subjects must be at least two years post-menopausal (subjected reported menopausal status), surgically sterile (bilateral tubal ligation, hysterectomy, or bilateral oophorectomy at least 6 months prior to first study drug administration), or willing to either (1) utilize hormonal contraception plus one barrier method or (2) use two barrier methods of contraception (e.g. diaphragm and spermicide) from initial screening until one month after taking the final dose. An intrauterine device (IUD) is considered a barrier method of contraception in this study. Male subjects must be willing to inform female partners of their participation in the study and must agree to use adequate contraceptive methods (vasectomy performed at least 6 months prior to first study drug administration, or use at least one barrier method of birth control) from initial screening until 1 month after taking the final dose.
6. Able to understand and comply with the study procedures, voluntarily agree to participate in this study, read the informed consent document, and provide written informed consent prior to start of any study-specific procedures. If the subject is unable to read the consent form and provide written consent, a legally authorized representative of the subject may read and sign the informed consent and the subject must verbally assent to participation.

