11.3 Analysis Populations

The primary efficacy population will be the intent to treat (ITT) efficacy population, which will include all randomized subjects who received at least one dose of treatment and returned for at least one follow-up visit. The per protocol (PP) population (randomized subjects who received at least one dose of treatment and returned for at least one follow-up visit with no significant protocol violations) and the completers (CP) population (randomized subjects who completed all 13 weeks of treatment with no significant protocol violations) will be used to evaluate the robustness of the ITT results.

The Safety population will include all randomized subjects who received at least one dose of study treatment.

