11.4 Efficacy: Cognitive Testing Analysis

Change from baseline will be calculated for the primary and secondary efficacy parameters at each time point and descriptive statistics provided for each time point. Summary plots of these data will also be provided. For RBANS DMI and total score, MMSE score, and ADCS-ADL total score, pairwise differences in change from baseline between the treatment groups (10 mg vs 25 mg BPN14770, 10 mg BPN14770 vs Placebo, 25 mg BPN14770 vs Placebo) will be assessed using an analysis of covariance (ANCOVA) model that includes baseline as a covariate and factors for week, site and treatment and the interaction term for week and treatment ; the pairwise differences will be assessed at each time point. CDR sum of boxes will be analyzed in the same manner.

Change from baseline in the other RBANS index scores (immediate memory, visuospatial/constructional, attention, language) will be summarized by time point, with descriptive statistics provided.

The composite endpoint will be based on the AD Composite Score (ADCOMS), a composite clinical outcome for prodromal Alzheimer's disease trials.²⁰ The composite endpoint and analysis model will be fully specified in the statistical analysis plan.

The efficacy analyses will be performed on the ITT, PP and CP analysis populations.

Supplemental analyses assessing treatment effect relative to severity of disease based on baseline MMSE score may also be performed.

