11.5 Safety Analysis

Safety analysis will be based on all subjects receiving at least one dose of study medication. Treatment emergent AEs will be summarized based on the frequency of AEs and their severity for all dosed subjects. All AEs will be coded using Medical Dictionary for Regulatory Activities (MedDRA) and summarized by treatment group and for the combined BPN14770 groups using preferred term and primary system organ class. Overall safety and tolerability will be assessed by clinical and/or statistical review of all safety parameters including adverse experiences, laboratory values, vital signs, physical exams, C-SSRS, and ECG data. General clinical and laboratory adverse events will be presented in frequency tables. Summary statistics (n, mean, SD, median, and range (minimum, maximum) will be tabulated for the observed values and the change (or percent change) from baseline for all continuous parameters for vital signs, ECG, and laboratory tests.

For each AE, the difference in incidence rates between each BPN14770 dose group will be compared to the placebo group using a Fisher's exact test.

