3.3. Subject Selection

Individuals are eligible for the study if they meet all of the inclusion and none of the exclusion criteria. The inclusion/ exclusion criteria will be assessed during Screening, which will be up to 28 days prior to first

This document is confidential.

study drug administration. Continued subject eligibility will be verified on Baseline at Baseline, prior to randomization. Specifically, subjects must meet the following AD criteria:

- Clinical Dementia Rating (CDR) score of 0.5 or 1 (on a scale from 0 to 3, with higher scores indicating worse outcome), with Memory Box score of 0.5 or greater.
- MMSE score of 20 or greater (range 0 to 30, with lower scores indicating worse outcome)
- RBANS DMI score < 85 (range 40 to 160, with lower scores indicating worse outcome)

See Sections 6.2 and 6.3 in the study protocol for the complete list of all eligibility criteria.

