5.4. Modified Intent-to-Treat Population

The modified Intent-to-Treat (mITT) Population will include all randomized subjects who received at least one dose of treatment and returned for at least one follow-up visit with the primary endpoint collected (non-missing). Subjects will be analyzed according to randomized treatment. The mITT Population will be used for all analyses of efficacy endpoints.

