8.1. Primary Efficacy Endpoint and Analysis – RBANS DMI

The Repeatable Battery for the Assessment of Neurological Status (RBANS) [Randolph 1998] is a brief, individually administered test measuring attention, language, visuospatial/constructional abilities, and immediate and delayed memory. It consists of 12 subtests, which yield five Index scores and a Total Scale score.

Total scores are calculated by adding up the scores for each of the 12 individual subtests and ranges between 0 and 311, where a low score indicates greater impairment. The range of possible scores for the RBANS DMI is 40 to 160.

The primary efficacy outcome measure is the change from baseline to Week 13 in the delayed memory index of the RBANS [Repeatable Battery for the Assessment of Neurological Status - Delayed Memory Index (RBANS DMI)]. Observed cases data (with no imputation for missing values) will be used for primary efficacy analysis.

The original RBANS DMI score and change from baseline will be summarized by treatment group at each time point.

The primary method of analysis will be an MMRM with restricted maximum likelihood estimation, an unstructured covariance matrix, and the Kenward-Roger approximation for denominator degrees of freedom. The model will include fixed effects for treatment, visit (time), the treatment-by-time interaction, ApoE4, pooled study site, the baseline RBANS DMI score as covariate, and a random effect for subject. [Similar models will be defined for the other continuous secondary efficacy endpoints.] Primary inferences will be drawn from treatment differences in the LSmean changes from baseline derived from the MMRM models at Week 13. As additional supportive information, treatment differences for Weeks 1, 4, and 8 will also be derived using the MMRM model. Least Squares Means for each visit and the SE of the LSMeans will be displayed graphically.

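### SAP Section 12 reports no meaningful changes, yet the SAP leaves out the protocol's Fisher's exact test of adverse events and makes four other kinds of undeclared change

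*SAP*

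**What the plan says.** SAP Section 12 consists of one statement: "There were no meaningful changes from the protocol described analysis". The two documents compare as follows.

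- **Adverse events.** Protocol 11.5, like the synopsis, says that for each adverse event "the difference in incidence rates between each BPN14770 dose group will be compared to the placebo group", by Fisher's exact test. SAP 11.3 lists its TEAE tables as numbers and percentages of subjects and names no between-arm test.
- **Primary model.** Protocol 11.4 has an ANCOVA with baseline, week, site, treatment and week-by-treatment. SAP 8.1 has an MMRM fitted by REML, with unstructured covariance, Kenward-Roger degrees of freedom, a random subject effect and an ApoE4 term. Sites are pooled by US time zone (SAP 6.5).
- **Primary population.** Protocol 11.3: "The primary efficacy population will be the intent to treat (ITT) efficacy population", meaning randomized, dosed at least once and seen at one follow-up visit or more. SAP 5.4 defines an mITT population in which the subject must also have "returned for at least one follow-up visit with the primary endpoint collected (non-missing", and uses it for all efficacy endpoints. SAP 5.7 still speaks of ITT results.
- **PP and CP analyses.** Protocol 11.4 commits to running the efficacy analyses on ITT, PP and CP. SAP 8.2 runs PP and CP for secondary endpoints only if the mITT population is larger by 10% or more.
- **Other analyses.** The other RBANS indices are descriptive in protocol 11.4 and modelled in SAP 8.2.1. CGI-I is listed under change from baseline in protocol 4.4.2.2 and under observed values in SAP 4.2. SAP 8.3 adds a fixed testing order that the protocol does not have.
- **Week 2.** Protocol 11.4: "the pairwise differences will be assessed at each time point". SAP 8.1, for the primary endpoint: "treatment differences for Weeks 1, 4, and 8 will also be derived using the MMRM model", besides Week 13.
- **DMI entry cut.** SAP 3.3 gives "RBANS DMI score < 85 (range 40 to 160, with lower scores indicating worse outcome"; protocol 6.2 admits scores up to and including 85.

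**The concern.** Section 12 is where a reader of the study report would look to learn how the analysis moved away from the protocol. If it says nothing of note changed when several things did, the reader has to find the differences by comparing the two documents, and has no record of when each was decided or why.

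Two consequences are practical. Programmers work from the SAP, so a protocol-specified safety comparison would not be produced. And the covariance structure, degrees of freedom and covariates determine the standard error and p-value of the primary comparison, so a change in them should be on record as made before unblinding. SAP 6.5 makes the timing question concrete: it states how many sites had enrolled and how small most were, so the pooling rule was written once enrolment by site was known.

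**Working it through.** **1. The plan's own figure.** Inputs from SAP 3.4: 80 per group, difference 7.15, SD 16, two-sided alpha 0.05. Standardized difference = 7.15/16 = 0.447. Noncentrality = 0.447 × √(80/2) = 2.83. Power is 0.807 by the normal approximation and 0.802 by the two-sample t-test, against the stated 80%. All 12 sample sizes in Table 1 reproduce exactly with the t-test. The sample size stands, and nothing below alters it.

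**2. What the missing test would show.** Take 85 subjects per arm and an event seen only on one dose. The two-sided Fisher p-value for k subjects against 0 is 2 × C(85,k)/C(170,k).

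- k = 5: 2 × (85·84·83·82·81)/(170·169·168·167·166) = 2 × 0.0294 = 0.059.
- k = 6: the one-sided value is multiplied by 80/165, giving 2 × 0.0143 = 0.029.

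The test would therefore first fall below 0.05 at 6 against 0. This describes how the test behaves at the planned size; it does not predict the results.

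**3. Primary model.** The protocol's ANCOVA already contains week and week-by-treatment, so it is a longitudinal mean model. What the SAP adds is the within-subject covariance, the degrees-of-freedom method, the random subject effect, the ApoE4 term and the replacement of individual sites by pooled ones. The treatment, week and baseline terms are common to both.

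**4. Population.** The two definitions differ only for a dosed subject who returned but has no post-baseline DMI. In the primary MMRM that subject supplies no outcome, so the primary estimate is essentially the same under either definition. For a secondary endpoint it is not: a subject with a post-baseline MMSE, ADCS-ADL or CGI-I but no DMI is in the protocol's population and outside every SAP efficacy analysis. The documents do not allow the number of such subjects to be estimated.

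**5. Secondary analyses.** If the mITT population exceeds PP and CP by less than 10%, SAP 8.2 says the secondary analyses on those populations will not be done. The protocol has no such condition. For the primary endpoint, SAP 8.1.2 keeps PP and CP.

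**6. Week 2.** RBANS is collected at Week 2 (protocol 8.12 and both schedules). Within SAP 8.1, scores and changes are summarized at each time point and LS means are plotted for each visit. The example code requests differences for the treatment-by-visit means, which covers every modelled visit. SAP 8.2.1 keeps pairwise differences at each time point for RBANS total. The sentence naming Weeks 1, 4 and 8 is therefore at odds with the rest of the SAP as well as with the protocol.

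**7. DMI cut.** SAP 3.3 refers the reader to protocol 6.2 and 6.3 for the full criteria, and SAP 5.8 defines a deviation as a departure from the procedures in the protocol. A score of exactly 85 meets the protocol's criterion, so it is not a deviation under either document.

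**The case against.** The sponsor has a fair reply on several items.

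- Section 12 says no *meaningful* changes; it does not claim that nothing changed. The MMRM keeps the protocol's longitudinal structure, ApoE4 is the randomization stratum, and SAP 6.5 explains the pooling: 38 sites, nearly 75% of them with fewer than 10 subjects. CGI-I has no baseline, as SAP 8.2.5 notes, so analysing observed values is sensible. This stands as a defence of the choices. It does not excuse leaving them undeclared.
- Counts and percentages by preferred term remain in the tables, so an imbalance of 6 against 0 would still be visible. The protocol's test is per event and unadjusted for multiplicity, so its p-values are only a screening aid. That limits the loss, but the protocol promised the test and the SAP gives no reason for leaving it out.
- The mITT definition hardly touches the primary estimate. That stands; its effect is on the secondary endpoints.

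Some stronger readings are tempting, but the documents do not support them.

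- A reader might infer that Week 2 is lost from the report. One sentence omits it; the summaries, plots and code include it.
- A reader might infer that a subject scoring 85 becomes a major eligibility deviation. SAP 5.8 measures deviations against the protocol, so this does not follow.
- A reader might count the modified ADCOMS as another undeclared change. Protocol 11.4 left the composite and its model to be specified in the SAP, and SAP 8.2.6 does so with a reason.
- A reader might infer that the changes were made with knowledge of treatment. Site enrolment counts are available without unblinding, and nothing in the documents shows that any choice followed unblinding. What is missing is a record.

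**Conclusion.** The statement in SAP Section 12 is inaccurate. The clearest case is the Fisher's exact comparison, the only adverse-event test the protocol names, which does not appear in the SAP. The primary model specification, the mITT population, the conditional PP and CP analyses, and the changes to the RBANS indices, CGI-I and testing order are also undeclared.

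The practical size is moderate. One protocol-specified safety comparison would go unproduced, and some secondary analyses may not be run. The primary estimate should be little affected by the population change. The effect of the model changes on its standard error cannot be computed from the documents. The Week 2 sentence and the DMI cut are wording mismatches; the latter has no effect on enrolment or deviations.

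This rests on the SAP text available, which lacks the front pages and Section 5.2. The safety and efficacy sections relied on here are present.

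**What to change.** 1. **SAP 11.3:** add the protocol's Fisher's exact p-values for each dose against placebo to the TEAE table by preferred term, with a footnote that they are unadjusted for multiplicity. Alternatively, declare and justify their removal in Section 12.
2. **SAP 8.1:** name Weeks 1, 2, 4 and 8.
3. **SAP 3.3:** use the protocol's wording for the DMI cut. In **SAP 5.7**, refer to mITT.
4. **SAP 12:** replace the present sentence with a list covering:
   - the Fisher's test, if it is not restored;
   - the covariance, degrees of freedom, random subject effect, ApoE4 term and site pooling in the primary model;
   - ITT replaced by mITT;
   - the conditional PP and CP analyses of secondary endpoints;
   - the other RBANS indices, CGI-I and the testing hierarchy.

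   Give each item its reason and say whether it was decided before unblinding.

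The cost is SAP wording and one extra column in one safety table. No additional data are needed. The one drawback is a set of per-event p-values that must not be read as confirmatory.
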